9. STUDY ASSESSMENTS

All images taken from the study will be saved and shared to the Sponsor via a data-protected platform.

9.1 Clinical Photography (VISIA)

Digital images of the subject's face will be taken at baseline (pre-injection), week 4 (pre-touch up), and week 24.

Clinic staff needs to ensure subjects to have a clean face with no makeup and to remove any jewelry from the area to be photographed. Subjects will be provided with a headband to keep hair away from the face. Subjects will be instructed to adopt neutral expression (3/4 left, front, 3/4 right), closed-mouth smile (3/4 left, front, 3/4 right), and open-mouth maximum smiling expression (3/4 left, front, 3/4 right) for each photograph.

A total of 9 full-face digital images will be taken of each subject's face using the VISIA CR photo-station (Canfield Imaging Systems, Fairfield, New Jersey) with a Canon digital SLR camera (manufacture name, location) under the standard lighting condition.

9.2 Clinical Photography (Vectra 3D)

Three (3) dimensional images of the subject's face will be taken at baseline (pre-injection), week 4 (pre-touch up), and week 24.

Clinic staff needs to ensure subjects to have a clean face with no makeup and to remove any jewelry from the area to be photographed. Subjects will be provided with a headband to keep hair away from the face. Subjects will be instructed to adopt neutral, nonsmiling expression with their eyes gently closed, and in a relaxed positioned for each scan.

Photography will be performed using the Vectra H2 Imaging system (Canfield Scientific, Inc., Canfield, NJ). The Vectra H2 utilizes raised flash to provide raked lighting to better capture and view skin topography and contours. Its software allows 3D viewing of the images and quantitative assessment of 3D parameters of the face.

Change in volume on each cheek will be analyzed by the Vectra H2 software (left and right cheek separately).

Protocol Version 2:

This document contains confidential, proprietary information.

Protocol GLI.04.US.SL.015

CONFIDENTIAL

The 3D images will be uploaded to a secure database that can be accessed by the Sponsor remotely.

9.3 Ultrasound

Ultrasound measurements will be performed at baseline (pre-injection and immediately post-injection), week 4 (pre-touch up), and week 24. A single ultrasound measurement will be taken on each subject’s left and right cheek, at neutral expression and at maximum smiling. The placement of the ultrasound probe needs to be at the same location of the product injection and for both visits to ensure consistent assessment.

Ultrasound measurements will be performed using an 18 MHz GE Venue Fit or 42 MHz Vevo® MD ultrasonic transducer interfaced to a system. The probe will have a standard setting of gain, depth, and velocity scale to assess placement/depth of filler, size of filler aggregates, and vascularity around aggregates.

9.4 Self-Assessment Questionnaire

Subjects will complete self-assessment questionnaire at week 4 (day 28) and week 24 (day 168). See Appendix I: Self-assessment questionnaire.

10. STATISTICAL ANALYSIS

Data of completing subjects will be included for all statistical analyses. Descriptive statistical summary will be performed including N, mean, median, standard deviations, minimum, and maximum of values at all applicable time points and for both treatments.

For each study treatment, mean of the change from baseline will be estimated at applicable post-baseline time point. The null hypothesis, that the mean change from baseline is zero, will be tested using methods described in the Statistical Analysis Plan table.

The following will be calculated and reported for each evaluation parameter at applicable post-baseline time point:

$$\text{Percent mean change from baseline} = \frac{(\text{visit mean score} - \text{baseline mean score})}{\text{baseline mean score}} \times 100$$

$$\text{Percent of subjects improved/worsened} = \frac{(\text{number of subjects improved/worsened from baseline})}{\text{total number of subjects}} \times 100$$

Comparison between the study treatments will be made in terms of changes from baseline. The null hypothesis, that the mean change from baseline is equal between the 2 study treatments at post-baseline time point, will be tested using methods described in the Statistical Analysis Plan table.

Statistical Analysis Plan

Evaluation	Change from Baseline	Comparisons between study treatments	Notes/Interpretation
Ultrasound measurement ○ Aggregate size	Paired t-test; If normality fails, a Wilcoxon signed-rank test will be used.	Wilcoxon rank-sum test or sample t-test	N/A

Protocol Version 2:

This document contains confidential, proprietary information.

Volume change by 3D imaging analysis	Paired t-test; If normality fails, a Wilcoxon signed-rank test will be used.	Wilcoxon rank-sum test or sample t-test	A higher value reflects an improvement in skin volume.
--------------------------------------	------------------------------------------------------------------------------	-----------------------------------------	--------------------------------------------------------

Questionnaires will be tabulated, and the percentage of all response options will be reported for each question.

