1. SYNOPSIS

Study Objective	To assess and compare tissue aggregation and visualization of two (2) Hyaluronic Acid fillers via ultrasound
Methodology	Randomized, split-face, subject-blinded, comparative study
Number of Subjects at the end	15 subjects to complete
Study duration	24 weeks
Test products	Restylane Contour Juvéderm Voluma
Conditions of use	Per on-label instruction
Study visits	Day 0, week 4, and week 24
Specific Inclusion Criteria:	
 ○ Demographics and study skin conditions - Any race and ethnicity (to be recorded) - Fitzpatrick skin type (to be recorded) - Women or men - Age: 22 to 65 years old - Subject with midface volume loss and contour deficiency ○ Administrative - Ability of giving consent for participation in the study - Agreement to adhere to the procedures and requirements of the study and to report to the institute on the day(s) and at the time(s) scheduled for the assessments.
Specific Exclusion Criteria:	
 ○ Skin conditions - History of allergy or hypersensitivity to lidocaine and/or injectable hyaluronic acid (HA) - Previous permanent or semi-permanent implant in proposed treatment area - Previous biodegradable tissue augmentation therapy in the proposed treatment area within 12 months prior to the baseline visit

Protocol Version 2:

This document contains confidential, proprietary information.

	
 - History of other facial treatment/procedure at the study area (midface) in the previous 6 months that would potentially interfere with study injections (e.g., facial surgery, oral surgery, resurfacing, mesotherapy, lipolytic injections, botulinum toxin injections)

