6. SELECTION AND DISPOSITION OF STUDY POPULATION

6.1 Number of Subjects

A minimum 15 subjects meeting inclusion/exclusion criteria listed below will be enrolled on the study to achieve 15 subjects who complete the study as planned.

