6.5.2. Prohibited Therapies

None other than as specified in the Inclusion/Exclusion criteria.

Protocol Version 2:

This document contains confidential, proprietary information.

Protocol GLI.04.US.SL.015

CONFIDENTIAL

The decision to administer a prohibited medication/treatment should be made with the safety of the subject being the primary consideration. Whenever possible, Galderma Laboratories, L.P. should be notified before the prohibited medication/treatment is administered to discuss possible alternatives.

If a subject receives prohibited therapy during the study, the subject may be allowed (at the discretion of the investigator / Galderma Laboratories, L.P.) to continue in the study for safety evaluation purposes, only.

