7.5 Treatments Administered

The study products contain lidocaine hydrochloride, but additional topical or local anesthesia or ice pack may be used at the discretion of the Investigator to enhance the experience of the subjects. Any additional topical or local anesthesia used will be recorded in the CRFs.

The injection tools (needles or cannulas) will be determined at the discretion of the Investigator. However, for each subject, the Investigator must use the same type of injection tool to perform injection for both sides of the face. Switching device within the subject will not be allowed in order to avoid any inconsistent comparison. Either needles or cannulas will be used per subject. The brand name, gauge and length of the cannulas and incision needles used by the Investigator will be recorded in the CRFs.

The study products will be injected into the midface at the supraperiosteal to subcutaneous layer in the prezygomatic space lateral to the plane of the medial canthus, along the plane of the zygomatic arch ~1cm medial to hairline (described in Figure 1 below).

Protocol Version 2:

This document contains confidential, proprietary information.

[figure not shown]

Figure 1. Description of injection boundary.

The amount of each study products needed varies between subjects and within subjects bilaterally, given the natural asymmetry of the face. However, subjects will be treated to optimal correction of the midface as agreed by the Investigator and subjects. The product volume injected during each treatment session for each subject will be recorded in the CRFs.

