8. STUDY PROCEDURES

There will be three (3) visits during the course of the study:

1. Visit 1 – Screening/Baseline/Day 0
2. Visit 2 – Week 4 (Day 28)
3. Visit 3 – Week 24 (Day 168)

Test design / flow chart	D0	W4	W24
Informed consent	X		
Photo consent	X		
Demographics/Med History	X		
Concomitant Meds.	X		
Inclusion and exclusion criteria	X		
Randomization	X		
Case report form (CRF)	X	X	X
Injection per on-label instruction	X		
Touch up (if applicable)		X	
Ultrasound	X*	X	X

Protocol Version 2:

This document contains confidential, proprietary information.

Protocol GLI.04.US.SL.015

CONFIDENTIAL

Standardized photography (2D and 3D)	X	X	X
Self-assessment questionnaire		X	X
AE Reporting	X	X	X

*Ultrasound at D0 will be performed before injection and immediately post-injection for each product.

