8.1.2. Visit 2 (Week 4 or Day 28 \pm 3 days)

1. Clinic staff or Investigator will record any AEs that are observed or reported.
2. Subjects will have the below assessments:
 - a. Clinical 2D photography by VISIA at neutral expression (3/4 left, front, 3/4 right), at closed-mouth smile (3/4 left, front, 3/4 right), and at open-mouth maximum smiling (3/4 left, front 3/4 right)
 - b. Clinical 3D photography by Vectra at neutral expression of full face
 - c. Ultrasound on each cheek at neutral expression and at maximum smiling (left and right). Note: ultrasound assessment will be performed at the same area from Visit 1.
 - d. Self-assessment questionnaire
3. Investigator will assess and offer the subjects an optional touch-up on the cheeks to reach the optimal aesthetic result.
4. If touch-up is needed, the same study treatment and type of injection tool used for each side of the face for the baseline treatment need to be used for this step. Investigator or Clinic staff will record the amount of the treatment used for the assigned cheek in the CRFs.
 - a. Touch-up treatment was not to be performed if the subjects have a disease or condition described in the exclusion criteria, or an ongoing treatment-related AE that in the opinion of the Investigator would be worsened by a touch-up treatment.
5. Once completed, subjects will be scheduled for a follow-up visit at Week 24 or Day 168 (\pm 3 days) and be dismissed from the Clinic.

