8.2 Discontinued Subjects

Any subject is free to discontinue his/her participation in this study at any time and for whatever reason, specified or unspecified, and without prejudice.

Protocol Version 2:

This document contains confidential, proprietary information.

Protocol GLI.04.US.SL.015

CONFIDENTIAL

An investigator may decide to discontinue a subject from the study for safety reasons or when it is in the best interest of the subject. Galderma Laboratories, L.P. may also decide to prematurely terminate or suspend the study or the participation of a subject in the study. All data gathered on the subject prior to termination should be made available to Galderma Laboratories, L.P.

Criteria for the discontinuation of a subject during the study will include the following:

- Adverse Event
- Lack of Efficacy
- Pregnancy
- Subject Request
- Protocol Violation
- Lost to Follow-up
- Any unmanageable factor, in the Investigator's opinion, that may significantly interfere with the protocol or interpretation of results.

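### All analyses are restricted to completing subjects, so valid post-injection and week-4 data of treated subjects who leave later would go unused

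*Combined protocol and SAP*

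**What the plan says.** Section 10 states "Data of completing subjects will be included for all statistical analyses". It defines no other analysis set, no missing-data method and no sensitivity analysis, and it does not say what completing means. The denominator for the percentage improved or worsened is not tied to a defined set either.

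Other sections suggest the meaning. The synopsis gives a duration of 24 weeks and a target of "15 subjects to complete". Section 6.1 says that a minimum of 15 subjects "will be enrolled on the study to achieve 15 subjects who complete the study as planned". Inclusion criterion 9 asks for agreement to attend every required visit, and Section 8 places the last visit at week 24.

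Outcome data are collected well before that. Both products are injected on Day 0. Ultrasound is done before and immediately after injection and again at week 4 before any touch-up (Section 9.3). 3D volume is measured at week 4, also before touch-up (Section 9.2), and the questionnaire is completed at the same visit (Section 9.4).

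Section 8.2 lists adverse event and lack of efficacy among the criteria for discontinuation. It adds: "All data gathered on the subject prior to termination should be made available to Galderma Laboratories, L.P". No planned analysis is assigned to those data.

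**The concern.** A week-4 estimate should not depend on whether the subject came back five months later. Under the completer rule it does: a subject with valid week-4 data on both cheeks is removed because of something that happened afterwards.

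There are two consequences.

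- **Selection.** If subjects leave because of a poor result or an adverse event, the completers are a favourable subset. The week-4 mean change within each product, the percentage improved or worsened and the questionnaire percentages can all be biased.
- **Lost information.** Each leaver takes a complete pair of cheeks out of the early comparison between products.

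In a split-face design a leaver removes both cheeks, so the products stay balanced in number. The comparison is biased only if leaving tracks one product's side, or tracks the worse side or the asymmetry when the products truly differ. In the first case the product whose poor results drive leaving looks better than it is; in the second the difference shrinks. Aggregate size has no stated favourable direction, so for that outcome the issue is lost data and a possible shift of either sign. Adverse-event recording under Section 11 is not limited to completers and is not in question.

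**Working it through.** The plan gives no dropout rate, alpha, power, effect size or SD, so its figure of 15 cannot be reproduced. What follows is illustration: 15 completers (from the plan) and k = 1 to 3 further treated subjects who leave after week 4 (assumed). Some dropout is plausible. With 15 enrolled and independent dropout assumed at 5% or 10%, the chance that all complete is 0.95^15 = 46% or 0.90^15 = 21%.

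**Pairs unused at week 4**, k/(15+k): 1/16 = 6.3%, 2/17 = 11.8%, 3/18 = 16.7%.

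**Percentages.** The completer rates are assumed. The other columns show all treated subjects with week-4 data if no leaver, or every leaver, responds.

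| Completers | k | No leaver responds | All leavers respond |
|---|---|---|---|
| 12/15 = 80.0% | 1 | 12/16 = 75.0% | 13/16 = 81.3% |
| | 2 | 12/17 = 70.6% | 14/17 = 82.4% |
| | 3 | 12/18 = 66.7% | 15/18 = 83.3% |
| 14/15 = 93.3% | 1 | 14/16 = 87.5% | 15/16 = 93.8% |
| | 3 | 14/18 = 77.8% | 17/18 = 94.4% |

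The first block suits a questionnaire item. The second suits the percentage improved in volume, which is probably high because "subjects will be treated to optimal correction of the midface as agreed by the Investigator and subjects".

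**Within-product mean change.** If leavers differ from completers by d SD, the completer mean differs from the all-treated mean by d × k/(15+k).

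- d = 0.5: 0.5 × 1/16 = 0.031 to 0.5 × 3/18 = 0.083 SD.
- d = 1: 1/16 = 0.063 to 3/18 = 0.167 SD.

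**Precision of the between-product comparison** (95% CI half-width). Both forms are shown because the analysis table does not name a paired test for this comparison.

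| N | Paired: t(0.975, N−1)/√N, in SD of the difference | Two-sample: t(0.975, 2N−2) × √(2/N), in SD of single-cheek change |
|---|---|---|
| 15 | 0.554 | 0.748 |
| 16 | 0.533 | 0.722 |
| 18 | 0.497 | 0.677 |

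Width with 15 pairs relative to 16 and 18: 1.04 and 1.11 paired; 1.04 and 1.10 two-sample.

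**Between-product shift** (simulation). The two cheeks are bivariate normal with SD 1 and correlation 0.3, 0.5 or 0.7. One or three subjects leave, namely those with the highest leaving propensity. Propensity is w × standardised score + noise of SD √(1−w²), with w = 0.3, 0.5 or 0.7. The table shows completers minus all treated, product A minus product B, in SD of single-cheek change.

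| What drives leaving | True difference | Shift |
|---|---|---|
| Nothing (random) | 0 | 0.00 |
| Poor result on A's side | 0 | +0.01 to +0.14 |
| Worse side | 0 | 0.00 |
| Worse side | 0.5 | −0.01 to −0.06 |
| Asymmetry | 0 | 0.00 |
| Asymmetry | 0.5 | −0.02 to −0.15 |

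With noise of SD 1 instead, the largest shifts fall to 0.11, 0.05 and 0.12 for one-sided, worse-side and asymmetry-driven leaving.

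**The case against.** **The reading is inferred.** Section 10 does not mention week 24, and its promise of N at all applicable time points would fit completion of each visit. The synopsis also speaks of study completion under its week-4 entry. This stands in part: week 24 is the likelier reading, not a certain one. If a per-visit rule is meant, the plan should say so, because an undefined term leaves the set and the denominator open until the data are seen.

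**The effect is small and conditional.** This stands. The worst simulated shift, 0.15 SD, needs three leavers, the strongest outcome dependence, correlation 0.3 and a true difference of 0.5 SD. At that correlation the SD of the difference is √(2 × 0.7) = 1.18, so the paired half-width with 15 pairs is 0.554 × 1.18 = 0.66 SD. The shift is therefore about 23% of the paired half-width, or 20% of the two-sample one (0.75 SD). With one leaver the largest shift is 0.07 SD.

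**Leaving for lack of efficacy may be rare.** Treatment is given on Day 0, with no continuing course to stop, and at week 4 "Investigator will assess and offer the subjects an optional touch-up on the cheeks to reach the optimal aesthetic result". This may reduce such leaving. It does not alter week-4 imaging and ultrasound values, which are recorded before the touch-up.

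**Enrolment aims at 15 completers.** It does, so the lost precision is a forgone gain and not a shortfall. Enrolling beyond 15 to reach that target is also what produces treated leavers whose early data go unused.

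**Conclusion.** The concern holds, as an improvement that should be made and not as a flaw that undermines the study. On the likelier reading, the plan's only analysis-set rule leaves out post-injection and week-4 data that are valid, already collected and passed to the sponsor, and nothing elsewhere brings them back.

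The size rests on assumed dropout. One to three later leavers cost 6% to 17% of week-4 pairs and make the interval about 4% to 11% wider than it need be. Within-product means move by 0.03 to 0.17 SD if leavers differ from completers by 0.5 to 1 SD. The between-product shift is zero under random dropout and reaches 0.14 to 0.15 SD only in the most extreme settings examined. With no leavers the results are identical, and the week-24 analysis is essentially unchanged in any case. Confidence is medium because completing is undefined and the dropout rate is unknown.

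**What to change.** Replace the sentence in Section 10 with wording such as:

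> All randomised and treated subjects are analysed at each time point at which they have data (both cheeks for the between-product comparison). The denominator for percent improved or worsened is the number of these subjects with data at that visit. For a subject who receives a prohibited therapy (Section 6.5.2), data before that therapy are analysed, later data are left out of the efficacy analyses, and the number left out is reported. A sensitivity analysis is restricted to completers, defined as subjects who complete week 24, other than those kept for safety evaluation only.

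Report the number of discontinuations and their reasons by visit.

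The prohibited-therapy sentence is needed because Section 6.5.2 allows such subjects "to continue in the study for safety evaluation purposes, only"; without it, the wider analysis set would conflict with that restriction.

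The cost is wording only, with no new visits or measurements. The one drawback is that N, and so the set of subjects, may differ between week 4 and week 24. The completer sensitivity analysis keeps the same-cohort comparison available.

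### The between-filler 3D volume comparison appears unpaired and ignores the Day 0 left-right asymmetry that Section 7.5 links to the amount injected; what is at stake is precision, not bias

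*Combined protocol and SAP*

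**What the plan says.** Section 7.5 (Treatments Administered) gives the reason for unequal volumes: "The amount of each study products needed varies between subjects and within subjects bilaterally, given the natural asymmetry of the face". The target is a result, not a fixed or equal volume: "subjects will be treated to optimal correction of the midface as agreed by the Investigator and subjects". The amount used is documented ("The product volume injected during each treatment session for each subject will be recorded in the CRFs"), but no analysis of it is described.

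Section 9.2 (Vectra 3D) provides a pre-injection image for every subject; images of the "face will be taken at baseline (pre-injection), week 4 (pre-touch up), and week 24". The endpoint is taken per side: "Change in volume on each cheek will be analyzed by the Vectra H2 software (left and right cheek separately").

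Section 10 sets the scale of the filler comparison: "Comparison between the study treatments will be made in terms of changes from baseline". For 3D volume, its table names "Wilcoxon rank-sum test or sample t-test" for that comparison. The neighbouring column, for change from baseline within one filler, names a paired t-test with a signed-rank fallback. No covariate, regression model or asymmetry measure appears anywhere in the document.

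Sections 7.4 and 8.1.1 assign product to side from a computer-generated list. No balancing on asymmetry is described. Section 6.1 plans for 15 completers.

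**The concern.** If the emptier cheek receives more gel, its 3D volume should rise more whichever filler it was given. Baseline asymmetry would then explain part of the within-subject difference in volume change, which is the natural quantity to compare in a split-face trial. A change score does not remove this. It subtracts each cheek's starting level, but not the extra correction that a more deficient cheek receives.

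Two things follow if the link is strong. The error of the filler difference is wider than it needs to be. And in a sample of 15, one product may happen to fall more often on the emptier cheek, which moves the estimate in that sample. The Day 0 image that could account for both is already taken, but the plan uses it only to form the change.

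**Working it through.** **Inputs.** From the documents: 15 completers, two cheeks each, side randomised. The documents state no alpha, power, effect size, SD or correlation, so there is no planned figure to reproduce. Assumed: two-sided 5% level; SD of the per-subject filler difference D set to 1; correlation r between baseline asymmetry A (Contour side minus Voluma side) and D varied from 0 to 0.7.

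**Chance imbalance.** Random side assignment gives A an expected mean of zero. Its sample mean has standard error 1/√15 = 0.26 SD of asymmetry. On the normal distribution:
- P(|imbalance| > 0.25 SD) = 2[1 − Φ(0.25 × √15)] = 33%
- P(|imbalance| > 0.5 SD) = 2[1 − Φ(0.5 × √15)] = 5%

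Unadjusted, r times the imbalance passes into the filler difference. At r = 0.5, a typical imbalance of 0.26 shifts it by 0.5 × 0.26 = 0.13 SD, and an imbalance of 0.5 shifts it by 0.5 × 0.5 = 0.25 SD.

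**Reference point.** With n = 15, a paired t-test has 80% power for a true difference of 0.778 SD of D (noncentral t, 14 degrees of freedom). The 0.25 SD shift is about a third of that (0.25/0.778 = 0.32).

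**Effect of adjustment.** Regress D on A and take the intercept, which is the product difference for a symmetric face. The variance ratio, adjusted to unadjusted, is (1 − r²)(n − 2)/(n − 3) = (1 − r²)(13/12). Power was simulated with 40,000 runs per row, from D = δ + rA + √(1 − r²)e with δ = 0.778.

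| r (assumed) | Variance ratio | Power, paired t | Power, adjusted |
|---|---|---|---|
| 0 | 1.08 | 80% | 77% |
| 0.2 | 1.04 | 80% | 78% |
| 0.3 | 0.99 | 80% | 81% |
| 0.5 | 0.81 | 80% | 87% |
| 0.7 | 0.55 | 80% | 96% |

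A separate simulation with 8,000 runs gave 88% at r = 0.5. With δ = 0, the type I error of both analyses was 4.8% to 5.1%. Adjustment breaks even where 1 − r² = 12/13, that is |r| = √(1/13) = 0.28.

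**Pairing.** The table above starts from a paired test, which Section 10 does not clearly specify. For scale, take a true difference of 0.75 SD of the per-side change and a within-subject correlation of 0.5 (both assumed). A two-sample t-test then has about 52% power and a paired t-test about 77%. At correlation 0 the order reverses slightly, 51% against 48%.

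**The case against.** The strongest reply is that nothing here is an error. Side is randomised, so the unadjusted comparison is unbiased, and chance imbalance is already part of the standard error of the paired difference. That stands. A reader might infer from Section 7.5 that the filler comparison is biased towards whichever product lands on the emptier cheek. The documents do not support this: asymmetry balances in expectation, and the simulated type I error of the unadjusted paired test stays near 5%.

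A second reply is that the gain rests on a correlation the documents do not give. That also stands. Section 7.5 says amounts vary with asymmetry, but it also leaves the end point to agreement between investigator and subject, so asymmetry is not the only influence. Below |r| of about 0.28, adjustment loses a little.

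Third, the 80% baseline is a convenience. A reader might take the table as this trial's power, but the plan claims none, and the pairing question is probably the larger one. For that reason the adjustment should accompany a paired result, not replace it.

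Fourth, the reach is limited. The stated objective in Section 5.1 is tissue aggregation and visualization by ultrasound; this point touches only the 3D volume comparison.

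Finally, Section 9.2 says of the imaging system: "Its software allows 3D viewing of the images and quantitative assessment of 3D parameters of the face". That is not a statement that it can give a left-right volume asymmetry from a single image, so feasibility has to be confirmed.

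None of these replies favours unpaired tests for a split-face comparison, and the choice of covariate follows from the protocol's own reasoning.

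**Conclusion.** The point holds as a matter of precision for the 3D volume endpoint. The plan appears to set aside the split-face pairing, and it makes no use of a pre-injection covariate that its own Section 7.5 suggests is relevant. The conclusion that the between-filler tests are unpaired rests on how the table reads: rank-sum is a test for independent groups, while the t-test named beside it does not say which form is meant.

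Over a paired t-test at 80% power, the covariate would add about 7 to 8 points if r is 0.5 and about 16 points if r is 0.7, make no real difference near 0.3, and cost about 3 points at 0. These figures assume n = 15, a two-sided 5% level, normal data, a linear relation and the stated range of r. The documents cannot say where in that range this trial lies. The change is worth making because the possible loss is small and the possible gain is not.

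**What to change.** In Section 10, for 3D volume at Week 4 and, separately, at Week 24:

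1. Make the between-filler comparison a within-subject analysis of the per-subject difference in volume change, Contour side minus Voluma side. Use a paired t-test or, if normality fails, a Wilcoxon signed-rank test.
2. Add a pre-specified linear regression of that difference on baseline left-right cheek volume asymmetry from the Day 0 pre-injection 3D image. Report the intercept with its 95% CI next to the unadjusted paired result. Fit it separately at each visit, because the Week 4 touch-up may alter the relation by Week 24.
3. Fix the facial region and reading method in advance, and confirm that the software can produce the measure.
4. Have asymmetry read as left minus right by a reader masked to side assignment. Apply the product sign afterwards from the randomisation list. The study is blinded for subjects only, so the masking of this reader has to be written in.
5. Do not adjust for injected volume. It is set after assignment and may itself depend on the product.

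The cost is SAP wording, one additional reading of each of the 15 Day 0 images (if the software allows it), one degree of freedom in the regression, and about 3 points of power in the adjusted analysis if asymmetry proves irrelevant. The unadjusted paired result is reported in either case.
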